4.7.6 Laboratory Data

All laboratory parameters will be assessed by a central laboratory, with the exception of the results of urine pregnancy tests, which will be determined locally and will be recorded in the eCRF.

All parameters will be graded according to NCI CTCAE (CTEP 2010), version 4.03, if applicable. Laboratory parameters that cannot be graded according to NCI CTCAE version 4.03 will be assessed with respect to normal range (low, normal, high).

The following laboratory parameters will be collected:

- Hematology: complete blood count with platelet count and automated differential, i.e. hemoglobin, hematocrit, platelet count, red blood cell count, RBC morphology, white blood cell count, absolute differential count (neutrophils, bands, eosinophils, lymphocytes, monocytes, basophils), MCH, MCHC, MCV,
- Serum chemistry: albumin, alkaline phosphatase, ALT, AST, direct bilirubin*, total bilirubin, calcium, cholesterol, creatine kinase, creatinine, triglycerides, gamma-glutamyl transferase, glucose, lactic dehydrogenase*, magnesium, phosphorus*, potassium, sodium, urea nitrogen, serum uric acid*, and amylase, C-reactive protein (N HS)-PS* (CRP), Creatinine clearance rate*, calculated using the Cockcroft-Gault formula
- Serum pregnancy test*,
- Urine dipstick for pregnancy testing*(local).

* = for these parameters no grading as per NCI CTCAE, version 4.03 is possible.

Hemoglobin A1c (HbA1c) was planned to be collected according to the initial version of the Clinical Study Protocol (CSP), but was removed in Amendment 3 of the CSP as not specifically relevant for this patient population. HbA1c values are continuously reported by the central laboratory, but will not be presented in any summary presentations. HbA1c values will only be listed.

Clinical laboratory values will be presented separately for CTCAE-gradable and non-CTCAE gradable parameters by laboratory panel (hematology, serum chemistry).

Serum or urine pregnancy data will only be listed.

For laboratory analyses, visits will be assigned to visit windows as described in Section 4.9. This will also be valid for possible unscheduled visits. In case that multiple evaluable assessments occur within the same visit, the most extreme value will be used for analyses.

**Pirfenidone and nintedanib —F. Hoffmann-La Roche Ltd
Statistical Analysis Plan MA29895, Version 1.0, final, 21 November 2016**

The following summaries will be prepared:

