4.7.3 Adverse Events	Updated definition for major adverse cardiac event (MACE): Specific terms from SMQs Arrhythmia related investigations, signs and symptoms, Cardiac arrhythmia terms (incl bradyarrhythmias and tachyarrhythmias), Cardiac arrhythmias, Cardiac failure: Cardiac arrest, Cardiac death, Cardio-respiratory arrest, Sudden cardiac death, Sudden death, Ventricular asystole, Agonal rhythm, Sinus arrest, Pulseless electrical	Need to specify terms.

	activity, Torsade de pointes, Ventricular fibrillation, Ventricular flutter, Ventricular tachycardia, Cardiac fibrillation, Cardiac flutter	
	Retching and Somnolence were deleted from the basket for photosensitivity reaction or rash	Terms also belong to other AE baskets
	'All and related elevated liver test results leading to treatment discontinuation' was deleted from the safety summary output.	The link between liver test results and respective AEs not established.
	'Number of events' was removed from the safety overview table.	Numbers of events are presented with the 'by SOC and PT' outputs
	Categories of TEAEs that are presented separately by SOC and PT specified in detail.	Description was not specific.
	Categories of TEAEs leading to treatment discontinuation specified in detail.	Description was not specific
	Analysis of timing of TEAEs added.	Not included in previous version.
4.7.6 Laboratory data	Paragraph added describing grading of laboratory values as per NCI CTCAE, when criteria for grading conflict with normal ranges as per central laboratory. Safety assessment of creatinine values changed from NCI-CTC grading to non-NCI-CTC grading.	Not included in previous version.
4.7.6 Laboratory data	Paragraph added on handling of values below the limit of quantification	Not included in previous version.
4.7.9 Previous and Concomitant medication	Note added that previously administered Pirfenidone will be presented separately.	Presented with previous/concomitant medications, previously.
4.8 Missing Data	Description added for imputation of missing start dates for previously administered Pirfenidone.	Presented with previous/concomitant medications, previously.
Appendix 5 Calculation of GAP Index Categories	Description of derivation of GAP Index added.	Not included in previous version.

TABLE OF CONTENTS

SIGNATURE PAGE.....	2
STATISTICAL ANALYSIS PLAN AMENDMENT RATIONALE.....	3
1. BACKGROUND	11
2. STUDY DESIGN	11
2.1 Protocol Synopsis.....	12
2.2 Outcome Measures	12
2.2.1 Primary Efficacy Outcome Measures	12

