4.7.6 Laboratory Data

All laboratory parameters will be assessed by a central laboratory, with the exception of the results of urine pregnancy tests, which will be determined locally and will be recorded in the eCRF.

All parameters will be graded according to NCI CTCAE (CTEP 2010), version 4.03, if applicable. Laboratory parameters that cannot be graded according to NCI CTCAE version 4.03 will be assessed with respect to normal range (low, normal, high).

For laboratory parameters and specific age ranges, the upper limit of normal provided by the central laboratory might be higher than the criterion for Grade 1 in NCI CTCAE. In such cases, the definitions provided in the NCI CTCAE, version 4.03 will be followed. This means that a shift of a laboratory value above the ULN that corresponds to a grade 2 abnormality or higher will be reported as such. Grade 1 abnormalities will not be reported for such situations.

Laboratory values that are reported to be below the limit of quantification (e.g. '<2') will be considered as to be 'LOW' for presentation in shift tables, if the value (e.g. '2') equals the lower limit of normal. The value as such (e.g. '2') will be used for descriptive statistics.

The following laboratory parameters will be collected:

- Hematology: complete blood count with platelet count and automated differential, i.e. hemoglobin, hematocrit, platelet count, red blood cell count, RBC morphology, white blood cell count, absolute differential count (neutrophils, bands, eosinophils, lymphocytes, monocytes, basophils), MCH, MCHC, MCV,
- Serum chemistry: albumin, alkaline phosphatase, ALT, AST, direct bilirubin*, total bilirubin, calcium, cholesterol, creatine kinase, creatinine*, triglycerides, gamma-glutamyl transferase, glucose, lactic dehydrogenase*, magnesium, phosphorus*, potassium, sodium, urea nitrogen, serum uric acid*, and amylase, C-reactive protein (N HS)-PS* (CRP), Creatinine clearance rate*, calculated using the Cockcroft-Gault formula
- Serum pregnancy test*,
- Urine dipstick for pregnancy testing*(local).

* = for these parameters no grading as per NCI CTCAE, version 4.03 is applicable.

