AEs will be coded to a preferred term and system organ class using the Medical Dictionary for Regulatory Activities (MedDRA). Laboratory abnormalities will be graded using the Common Terminology Criteria for Adverse Events (CTCAE). Prior and concomitant medications will be coded using the World Health Organization (WHO) Drug Dictionary.

Because this is a safety and tolerability study that is not designed to assess efficacy, no formal statistical hypotheses for efficacy will be assessed. The efficacy analyses will be limited to descriptive statistics.

Data summaries will be provided for baseline characteristics; patient disposition; extent of exposure; the number and proportion of patients who complete 24 weeks on pirfenidone at a dose of 1602–2403 mg/d and nintedanib at a dose of 200–300 mg/d (with 95% confidence interval [CI]); the numbers and proportions of patients with a dose reduction or a dose interruption; the number and proportion of patients who discontinued combination treatment because of a AE (with 95% CI); the total number of days on combination treatment at an pirfenidone dose of 1602–2403 mg/d and a nintedanib dose of 200–300 mg/d; the total number of days from the start of combination treatment to discontinuation of one or both study treatments; the final prescribed doses of pirfenidone and nintedanib; and the reasons for premature discontinuation of combination treatment.

AEs and SAEs leading to discontinuation will be summarized by incidence, severity, seriousness, and relationship to treatment. Additional summaries will be provided for the numbers and proportions of patients with a Major Adverse Cardiac Event (MACE), a cerebrovascular event, a bleeding event, or a thromboembolic event; the numbers and proportions of patients discontinuing combination treatment for a liver test abnormality, a GI event, or a photosensitivity reaction/rash; the numbers and proportions of patients with an emergency department visit or hospitalization; and deaths.

Observed and change values for clinical laboratory and vital signs data will be summarized. Grade 3 and 4 laboratory abnormalities will be summarized by CTCAE grade, and shift tables by CTCAE grade will be provided.

**Pirfenidone and nintedanib — F. Hoffmann-La Roche Ltd
Statistical Analysis Plan MA29895, Version 2.0, final, 17 May 2017**

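### SAP V2.0 section 4.7.6 drops CTCAE grading of creatinine without a reason that explains it and, separately, suppresses Grade 1 more widely than the ULN conflict requires

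*SAP*

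**What the plan says.** **Creatinine.** The general rule in V2.0 section 4.7.6 is "All parameters will be graded according to NCI CTCAE (CTEP 2010), version 4.03, if applicable"; parameters that cannot be graded are assessed against the normal range instead. In the chemistry list creatinine carries a star: "calcium, cholesterol, creatine kinase, creatinine*, triglycerides". The footnote to the star reads "for these parameters no grading as per NCI CTCAE, version 4.03 is applicable". In V1.0, section 4.7.6, with the same CTCAE version, the entry has no star, "calcium, cholesterol, creatine kinase, creatinine, triglycerides", and the footnote there reads "for these parameters no grading as per NCI CTCAE, version 4.03 is possible". The amendment rationale table at the front of V2.0 records the change: "Safety assessment of creatinine values changed from NCI-CTC grading to non-NCI-CTC grading". The rationale cell for that row says only that the content was absent from the previous version.

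Later in V2.0 section 4.7.6, the worst-grade shift tables and the Grade 3/4 counts are limited to CTCAE-gradable parameters. Other parameters get a low/normal/high shift table. All parameters get by-visit descriptive statistics, changes from baseline and listings.

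**Grade 1.** The same section covers parameters and age ranges, none of them named, for which the central laboratory's ULN lies above the CTCAE Grade 1 criterion. It says that the CTCAE definitions govern in that case and that values above the ULN of Grade 2 or more are reported. It then adds "Grade 1 abnormalities will not be reported for such situations".

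**The concern.** The study's primary objective is safety and tolerability, so its laboratory tables should separate small abnormalities from large ones.

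For creatinine they no longer do so by grade. A value just above the ULN and a value far above it fall into the same category of the shift table, and no severity count is planned. Creatinine clearance is also starred, so neither measure has a graded summary.

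For the parameters under the Grade 1 rule, the text says that CTCAE is followed and then leaves out one of its grades. The trigger is the parameter or age range, not the individual value. The rule therefore removes Grade 1 results that are abnormal by both standards along with those that the laboratory calls normal. It also does not say what happens to a Grade 1 value at baseline, so two programmers could build different shift tables from the same text.

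**Working it through.** The plan states no figure on either matter, so there is none to reproduce. The check is a comparison of texts for creatinine and an enumeration for Grade 1.

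**1. Creatinine, V1.0 against V2.0**

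- Starred chemistry parameters in V1.0: direct bilirubin, lactic dehydrogenase, phosphorus, uric acid, CRP, creatinine clearance (6).
- Starred chemistry parameters in V2.0: the same 6 plus creatinine (7).
- CTCAE version: 4.03 in both.
- Footnote: V1.0 reserves the star for parameters whose grading is not possible; V2.0 changes the word to applicable.

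The document thus treated creatinine as gradable and then chose not to grade it. The amendment row holds two changes: the new ULN/Grade 1 paragraph and the creatinine switch. Its rationale fits the first, which was new. It does not fit the second, because V1.0 did cover creatinine.

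**2. What creatinine loses and keeps under V2.0**

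- Lost: Grade 3/4 counts over time, the total of visits and patients with Grade 3/4 elevations, and the worst-grade shift table.
- Kept: descriptive statistics by visit (section 4 includes the maximum; section 4.7.6 takes the most extreme value in a window), change from baseline, the low/normal/high shift table and listings.

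**3. Grade 1 rule: which values it reaches**

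Let C be the Grade 1 criterion, U the laboratory ULN with U > C, and T the Grade 2 threshold. Assume U < T; the documents give none of the three.

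- C < x ≤ U: Grade 1 by CTCAE, normal for the laboratory. Not reporting it is defensible.
- U < x ≤ T: Grade 1 by CTCAE and above the ULN. Not reported under the rule as written.
- x > T: Grade 2 or higher. Reported.

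**4. Grade 1 rule: effect on the shift categories**

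There are 15 pairs of baseline and worst grade from 0 to 4 with worst ≥ baseline. Shift = worst − baseline. The plan's categories are shifts of one to four, three to four, and four grades. Reading A replaces Grade 1 by 0 at baseline and afterwards. Reading B replaces it only after baseline.

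| Pair | True shift | Reading A | Effect under A | Reading B |
|---|---|---|---|---|
| 0→1 | 1 | 0 | lost from one-to-four | 0, same loss |
| 1→2 | 1 | 2 | none on category | 1, correct |
| 1→3 | 2 | 3 | wrongly added to three-to-four | 2, correct |
| 1→4 | 3 | 4 | wrongly added to four | 3, correct |

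Under A, the other 11 pairs keep their shift size. Under B, the only change to a category is the 0→1 loss. Under both readings the number of patients at Grade 3 or 4 is unchanged, because neither grade is replaced.

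**The case against.** The creatinine change is disclosed in the amendment table, and a difference between V1.0 and V2.0 is not in itself an error. That creatinine can be graded is read from V1.0 and the amendment table, not from CTCAE, which is not at hand. The size of a rise remains visible, as set out above. A rise reported as an adverse event would be graded under section 4.7.3, urea nitrogen stays unstarred, and the iDMC reviews laboratory toxicities under section 4.10. All of this stands. A reader might infer that severe creatinine rises go uncounted altogether; the documents do not support that. What is lost is the count and the shift by grade.

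A reader might also take the synopsis in Appendix 1 as a broken promise: "Grade 3 and 4 laboratory abnormalities will be summarized by CTCAE grade, and shift tables by CTCAE grade will be provided". That sentence names no parameter, and it stood unchanged in V1.0 beside a list of ungraded parameters. It cannot have meant every analyte and is weak support.

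On Grade 1, nothing in the documents shows that any patient will have a value above the ULN and below Grade 2, and leaving out Grade 1 values that are normal for the laboratory is reasonable. This stands too, but the sentence is not limited to such values. Overcounted large shifts are a further tempting reading. They arise only if baseline Grade 1 is also set to 0, and the plan does not say that it is.

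Neither point explains the creatinine switch. One might guess, since both changes share a row in the amendment table, that the ULN conflict prompted it. Even then, the plan's own rule for that conflict keeps Grade 2 and above, so removing every creatinine grade goes further than needed.

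**Conclusion.** Both points hold in limited form, and they are independent of each other.

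(a) Following V2.0 gives no Grade 3/4 count and no grade-shift table for creatinine in any of the approximately 80 patients, for no stated reason that explains it. The loss is one of presentation by severity. The data and their size remain in other outputs.

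(b) The Grade 1 sentence leaves unreported any value above both the laboratory ULN and the Grade 1 criterion but below Grade 2, which conflicts with the statement that CTCAE governs. Shifts from 0 to 1 of this kind are lost. Misplacement of 1-to-3 and 1-to-4 changes is conditional on the unstated baseline handling. Creatinine, being ungraded in V2.0, is outside this rule, and no severe value of another parameter is hidden by it. The number of patients affected cannot be derived, because the parameters, age ranges and laboratory limits are not given.

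The primary outcome, the analysis of discontinuation for adverse events and the Grade 3/4 liver tables are unaffected. The changes are worth making because they are cheap and the study is about safety.

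**What to change.** In V2.0 section 4.7.6:

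- Keep the low/normal/high shift table for creatinine and add beside it the Grade 3/4 counts and the worst-grade CTCAE shift that V1.0 provided. If the sponsor prefers not to grade creatinine, the least that is needed is a reason in the amendment table that addresses creatinine.
- Replace the Grade 1 sentence with a rule on the value: Grade 1 is suppressed only when the value is at or below the laboratory ULN; a value above both the ULN and the Grade 1 criterion is Grade 1; the rule applies identically at baseline and post-baseline. Name the parameters and age ranges concerned.

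Make the two changes together, since a regraded creatinine could itself come under the Grade 1 rule if its laboratory ULN exceeds the criterion.

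The cost is a few sentences and a few table rows, with no new data. The small downside is that more low-grade abnormalities are displayed.

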4.7.7 Vital Signs

Vital signs, body weight and body temperature assessments will be assigned to visit windows as per Section 4.9. Descriptive statistics will be used to summarize vital signs data at baseline, at each scheduled post-baseline visit, and for the absolute change from baseline to each scheduled post-baseline visit. Line graphs for systolic and diastolic blood pressure will be provided. The body mass index (BMI) will only be calculated for the BMI at baseline and presented with the demographic data.

4.7.8 ECG

QTcF values will be assigned to the following intervals: < 500 ms, 500–550 ms, and > 550 ms. Numbers and proportions of patients with their maximum QTcF interval category will be summarized at Baseline, Week 24 or early discontinuation, EOT and Follow-up. Absolute changes from the Baseline to each post-baseline visit in QTcF values will be categorized to ≤ 30 ms, 31–60 ms, and > 60 ms. Numbers and proportions of patients in each category will be presented for each post-baseline visit. Planned visits will be used for presentations.

At each visit, the ECG result is to be assessed as being normal, abnormal - not clinically significant, abnormal - clinically significant, or unable to evaluate. Changes from baseline to each post-baseline visit will be presented showing numbers and proportions of patients in each combination of categories.

Descriptive statistics for heart rate and changes from baseline for each visit will be presented.

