Hemoglobin A1c (HbA1c) was planned to be collected according to the initial version of the Clinical Study Protocol (CSP), but was removed in Amendment 3 of the CSP as not specifically relevant for this patient population. HbA1c values are continuously reported by the central laboratory, but will not be presented in any summary presentations. HbA1c values will only be listed.

**Pirfenidone and nintedanib — F. Hoffmann-La Roche Ltd
Statistical Analysis Plan MA29895, Version 2.0, final, 17 May 2017**

Clinical laboratory values will be presented separately for CTCAE-gradable and non-CTCAE gradable parameters by laboratory panel (hematology, serum chemistry).

Serum or urine pregnancy data will only be listed.

For laboratory analyses, visits will be assigned to visit windows as described in Section 4.9. This will also be valid for possible unscheduled visits. In case that multiple evaluable assessments occur within the same visit, the most extreme value will be used for analyses.

The following summaries will be prepared:

For each laboratory parameter, descriptive statistics of laboratory values at each scheduled visit (derived as described above), and absolute changes from baseline to post-baseline will be presented.

Shift tables presenting changes from baseline to worst CTCAE grade, in the indicated direction, will be provided for CTCAE-gradable parameters. These changes will also be expressed as shifts of 1 to 4 grades, 3 to 4 grades and 4 grades. If no CTCAE grade is available for a specific laboratory variable, shift tables will present worst changes with respect to normal range category (low, normal, high).

For CTCAE-gradable parameters, numbers and percentages of patients with laboratory values of Grade 3 and 4 will be presented over time. Further, the total number of visits with Grade 3/4 elevations, as well as the number and percentages of patients with Grade 3/4 elevations for each parameter will be provided.

Liver abnormalities (total bilirubin, alkaline phosphatase, ALAT (SGPT), ASAT (SGOT)) of Grade 3 and 4 will be presented showing numbers and percentages of patients for each parameter separately, as well as in combination with at least one of the other parameters elevated post-baseline. Line graphs will also be provided.

All laboratory data will be listed.

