ECG data will be summarized, presenting the numbers and proportions of patients with a maximum QTcF interval < 500 ms, 500–550 ms, and > 550 ms; with a maximum change from the baseline QTcF interval of ≤ 30 ms, 31–60 ms, and > 60 ms; and with ECG changes considered by the Investigator to be clinically significant.

DETERMINATION OF SAMPLE SIZE

A sample size of approximately 80 patients was selected based on the AE discontinuation rates after one year observed in the randomized Phase 3 pirfenidone studies and the randomized Phase 2 and 3 nintedanib studies (pirfenidone 14.6%, nintedanib 21%; per the 2014 US labels). Given that for pirfenidone the discontinuation rate after 24 weeks was 6%-8% in studies PIPF-004 and PIPF-006 it is a reasonable assumption that the nintedanib discontinuation rate was around 10% - 11%. As in this study of combination treatment, it is possible that the addition of nintedanib to ongoing pirfenidone treatment could increase the proportion of patients who discontinue because of an AE, given the overlap in the GI and hepatic effects of the two medications.

Assuming 85% of the patients complete 24 weeks of combination treatment, a sample size of 80 patients would be expected to yield an actual completion rate of 77.2% to 92.8% using a 95% CI

Number of Patients who completed 24 weeks	Proportion of Patients who completed 24 weeks	Lower Bound of 95% CI	Upper Bound of 95% CI
76	95.0%	90.2%	99.8%
72	90.0%	84.4%	96.6%
68	85.0%	77.2%	92.8%
64	80.0%	71.2%	88.8%
60	75.0%	65.5%	84.5%

CI = confidence interval

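### Section 4.7.8 tabulates QTcF only by planned visit, so the per-patient maximum QTcF and maximum change promised in the synopsis are not produced

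*SAP*

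**What the plan says.** **The synopsis.** The protocol synopsis reproduced in Appendix 1 describes the ECG summary as "presenting the numbers and proportions of patients with a maximum QTcF interval < 500 ms, 500–550 ms, and > 550 ms", and also "with a maximum change from the baseline QTcF interval of ≤ 30 ms, 31–60 ms, and > 60 ms". Neither item is tied to a visit. Each reads as one classification per patient.

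**The analysis text.** Section 4.7.8 (Version 2.0) says: "Numbers and proportions of patients with their maximum QTcF interval category will be summarized at Baseline, Week 24 or early discontinuation, EOT and Follow-up". For change from baseline it says: "Numbers and proportions of patients in each category will be presented for each post-baseline visit". It then adds: "Planned visits will be used for presentations". Version 1.0 has the same wording.

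**Related rules.**
- Section 4.9 applies visit windows to vital signs and laboratory data. ECG is not among them.
- Sections 4 and 4.9 define EOT as the Week 24 data for completers and the early discontinuation visit for the others.
- Section 4.7.6 assigns laboratory results to windows, uses the most extreme value within a visit, and says of the window assignment: "This will also be valid for possible unscheduled visits". Section 4.7.8 has no counterpart.
- The schedule in Appendix 2 places the 12-lead ECG at Screening, Baseline, Day 168, Follow-up and early discontinuation.
- Section 4 says that all data recorded in the eCRF will be listed.

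**The concern.** For a drug-safety reader the useful QTcF figures are each patient's worst value and worst increase after combination treatment starts. The synopsis names both. The analysis text replaces them with visit-specific tables and declares no departure. Elsewhere the SAP does declare one: Section 4.7.9 says openly that the drug dictionary differs from the protocol. The amendment rationale for Version 2.0 lists no ECG change. The mismatch therefore looks like an oversight.

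Two things are at stake. The first is that a summary promised in the synopsis will be missing from the output. The second is that an ECG taken for clinical cause during the 24 weeks, if recorded, would have no place in any QTcF table. Safety and tolerability are the primary objective, and QTcF of 500 ms or more at Screening is an exclusion criterion, so the upper categories matter to this trial.

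**Working it through.** The plan gives no figure to reproduce. The check compares the sections and applies a counting bound.

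**Step 1: which planned ECGs feed the post-baseline tables.** From Appendix 2, each patient has at most one planned end-of-treatment ECG (Day 168 or early discontinuation) and one at Follow-up. EOT is the first of these under another label and adds no new measurement. That leaves at most two planned post-baseline values per patient.

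**Step 2: what the maximum means in Section 4.7.8.** The category is summarized at each named visit. With one ECG per planned visit, the maximum at a visit is simply that visit's value. The word would have an effect only if replicate ECGs were taken, which the SAP does not state. No row combines end of treatment with Follow-up.

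**Step 3: whether the promised count can be rebuilt.** Let a be the number of patients with a change above 60 ms at EOT, b the number at Follow-up, and N the number of patients. The number M whose maximum change exceeds 60 ms is the size of the union of the two groups:

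max(a, b) ≤ M ≤ min(N, a + b)

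The by-visit tables give a and b but not the overlap. As an illustration only, take a = b = 1 and N = 80:
- Same patient both times: M = 1, and 1/80 = 1.25%.
- Two different patients: M = 2, and 2/80 = 2.5%.

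Both cases give identical by-visit tables. The same bound holds for a QTcF above 550 ms, or of 500 ms and more. This part of the point needs no unscheduled ECG.

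**Step 4: where an unscheduled ECG would go.** Appendix 2 plans no ECG between Day 1 and Day 168, so any ECG in that interval for a patient still on treatment is unscheduled. Section 4.7.8 uses planned visits, Section 4.9 gives ECG no window, and EOT draws only on the Week 24 or early discontinuation visit. Such a value therefore has no slot in any QTcF table. It would still appear in the listings required by Section 4.

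**Step 5: direction of the effect.** A maximum over a subset of a patient's values cannot exceed the maximum over all of them. Leaving out unscheduled ECGs therefore either leaves the upper-category counts unchanged or lowers them. Each patient so missed would be 1/80 = 1.25 percentage points at the planned size. The SAP does not say how many unscheduled ECGs to expect, so no total can be given.

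**The case against.** **The planned-visit sentence may only be a programming instruction.** Since ECG has no windows, it can be read as telling the programmer to use the visit labels in the eCRF. A reader might infer that the SAP has a rule discarding unscheduled ECGs. No sentence says so. What stands is narrower: under either reading such an ECG has no table to enter.

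**Nothing shows that unscheduled ECGs exist in the database.** The SAP mentions unscheduled visits only for laboratory data. A reader might infer a known downward bias of 1.25 points. The documents do not support that: the figure is one patient in 80, applied to a number of cases that may be zero. It is conditional only.

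**The information is not lost.** Recorded ECGs are listed. Related clinical events reach the adverse event tables, and the MACE basket in Section 4.7.3 names terms such as torsade de pointes and ventricular tachycardia. This is fair, but neither a listing nor an event count is the QTcF summary that the synopsis describes.

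**The synopsis does not say that unscheduled ECGs count.** This is correct. Including them is a recommendation for a safety maximum. The laboratory rule shows that the SAP makes this choice elsewhere, but laboratory data have many more scheduled visits, so the comparison is only suggestive.

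**The gap is small.** On planned ECGs alone, what is missing is one row combining EOT with Follow-up, and QTcF is neither a primary nor a named secondary outcome. This limits the weight of the point but does not remove the mismatch.

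**Conclusion.** The point holds in two parts of different strength.

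The mismatch between Appendix 1 and Section 4.7.8 is plain from the text. The per-patient maximum post-baseline QTcF and maximum change are not produced, and the maximum-change count cannot be derived from the by-visit tables. This rests only on the two sections and the ECG schedule.

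The absence of any route for unscheduled ECGs is a close inference from Sections 4.7.8 and 4.9 and Appendix 2. If such ECGs were recorded, the tables can only understate the worst values. Whether they were, and how many, is unknown, so no bias is demonstrated and its size cannot be stated.

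No primary or named secondary result depends on these tables. It is a modest but worthwhile correction to a safety summary.

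**What to change.** Keep the by-visit tables on planned visits. In Section 4.7.8, replace the planned-visit sentence with wording such as: *By-visit tables use planned visits. In addition, each patient's maximum post-baseline QTcF category and maximum change-from-baseline category will be presented, using all recorded post-baseline ECGs, including any unscheduled ones.* The bands already in the section can be used as they stand.

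If the sponsor prefers to restrict the maximum to planned ECGs, the section should say so, still add the per-patient rows, and give the reason for setting recorded unscheduled values aside.

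The cost is a sentence or two and a few table rows, with no new data collection. The drawback is that unscheduled ECGs are not taken equally in all patients, so a patient with more ECGs has more chances of a high maximum. A footnote giving the number of patients with any unscheduled ECG would let the reader judge this.
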